### **3.6. Timing of the final analysis**

The final analysis for Trial I will be conducted only after 9 days have elapsed since the treatment of the final enrollee. The final analysis for Trial II will be conducted only after 7 months have elapsed since the treatment of the final enrollee. We anticipate at least two months for data processing and resolution of potential errors, anomalies, or missing values.

### **3.7. Timing of outcome assessments**

In Trial I, outcome assessments will be conducted each week since beginning of treatment, with a window of 5 to 9 days for the final outcome. In Trial II, outcome assessments will be conducted every 3 months since beginning of treatment, with a window of 5 to 7 months for the final outcome.

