3 OBJECTIVES AND ENDPOINTS

OBJECTIVES	ENDPOINTS	JUSTIFICATION FOR ENDPOINTS
Primary		
Specific Aim 1: To compare CMV viral load and inflammation after randomization to oral valganciclovir, topical ganciclovir, or placebo.	Reduction in log transformed viral load as measured by quantitative PCR at 7 days of treatment.	Viral load post 7 days of treatment using fluid from the eye is an important micro biologic outcome to compare the effect of treatment. This is primary outcome for Trial I
Specific Aim 2: To compare the effect of long-term antiviral suppression on recurrence of inflammation.	Proportion of participants with recurrence at the end of 6months.	CMV recurrence is a clinical outcome indicating effect of long-term treatment in controlling inflammation and preventing recurrence. This is primary outcome for Trial II
Specific Aim 3: To determine if antiviral resistance mutations develop with exposure to long-term antiviral suppression.	Prevalence of mutations associated with antiviral resistance	Using aqueous fluid from the eye, comparing prevalence of mutations conferring antiviral resistance in at baseline (Trial I) and recurrent disease (Trial II) is important to determine the relationship between viral and host genome features that mediate inflammation in CMV anterior uveitis.

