8 STATISTICAL CONSIDERATIONS

8.1 Statistical Hypotheses

Specific Aim 1 (Trial I): To compare CMV viral load and inflammation after randomization to 7 days of oral valganciclovir, topical ganciclovir 2%, or placebo.

1a: We hypothesize that participants randomized to oral valganciclovir will have a lower viral load after 7 days compared to those randomized to either topical ganciclovir 2% or placebo (Trial I primary outcome).

1b: We hypothesize that a greater proportion of participants randomized to oral valganciclovir will have controlled inflammation compared to those randomized to either topical ganciclovir 2% or placebo.

Specific Aim 2 (Trial II): To compare the effect of long-term antiviral suppression on recurrence rate of inflammation.

2a: We hypothesize that participants randomized to placebo will have fewer recurrences over 12 months compared to those randomized to either oral valganciclovir or topical ganciclovir 2% (Trial II primary outcome).

2b: We hypothesize that aqueous obtained at the time of a recurrence of inflammation will demonstrate a detectable viral load and will correlate with level of inflammation.

Specific Aim 3 (samples from Trials I and II): To characterize host transcriptional signatures and viral genomic features in CMV anterior uveitis using RNA sequencing of aqueous samples.

3a: We hypothesize participants completing both trials who exhibit recurrent inflammation after antiviral suppression (Trial II) will have a higher prevalence of CMV mutations associated with antiviral resistance compared to baseline samples (Trial I).

3b: We hypothesize that host transcriptional profiles will (i) distinguish CMV anterior uveitis from anterior uveitis cases negative for CMV and unable to enter Trial I, (ii) we will identify non-CMV pathogens in cases unable to enter Trial I, and (iii) identify unique signatures associated with recurrent inflammation in Trial II participants.

Primary Outcome:

- Viral load after 7 days of treatment (Trial I)
- Recurrence of inflammation over 12 months (Trial II)

Secondary outcomes:

- Anterior chamber cell (Trials I and II)
- Intraocular pressure (Trials I and II)
- Visual acuity (Trials I and II)
- Corneal endothelial cell count and morphology (Trials I and II)
- Number of glaucoma medications (ocular hypertensive medication) (Trials I and II)
- Prevalence of mutations conferring antiviral resistance (Trials I and II)

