**Primary analysis for Trial II.** The primary outcome for Trial II is the proportion of participants experiencing CMV recurrence over 12 months. We acknowledge that hypothesizing fewer recurrences in the placebo group compared to the oral antiviral group is contradictory to what one might think would typically occur with exposure to antivirals. However, data from a previous observational study showed a one-year recurrence risk of 25.0% (3/12) among participants who did not receive antiviral treatment and 75.0% (9/12) in participants receiving systemic antiviral treatment (oral ganciclovir or valganciclovir), which is similar to the experience of other research. Additionally, it is well documented that long-term suppressive-level dosing of antiviral in an immunodeficient host or in an immunologically privileged organ (such as the eye) can create an environment permissive to the development of antiviral resistance. Given 28 participants per arm (105 total from Trial I with 20% loss to follow-up) and a recurrence risk of 25% in the placebo group, we can detect a difference of 40 percentage points between the oral valganciclovir and the placebo groups (from 25% to 65%), using a two-sample z-test for proportions with 80% power and a two-sided alpha of 0.05/2.

**For Specific Aim 3,** we estimated the minimum detectable effect for the difference in prevalence of infections that have antiviral resistance mutations among recurrent infections in Trial II among patients who receive long-term antiviral prophylaxis compared with their infections at baseline. Aim 3 will focus on patients in the two active treatment arms in Trial II, because we would expect long-term use of topical and oral antivirals to lead to similar selection for antiviral resistance. From 117 patients enrolled, we conservatively assumed that 72% of patients would complete both Trial I and Trial II (n=84). We further assumed that 60% of patients will develop a recurrent infection over the monitoring period during the trials (Table 1). Participants who receive active treatment in Trial II (treatment regimens C+D) will contribute to the Aim 3 analysis (n=34). The analysis will be a paired analysis, comparing the proportion of recurrent infections with antiviral resistance mutations with that same proportion at baseline.

Table 1. Anticipated participant enrollment, and follow-up by treatment patterns

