## 6. Analysis

### 6.1. Outcome definitions

Trial I: Primary Endpoint: Log-transformed viral load after 7 days of treatment

Secondary Endpoints:

- Anterior chamber cell (days 7, 21)
- Intraocular pressure (days 7, 21)
- Visual acuity (days 7, 21)
- Controlled inactivity defined as  $\leq 0.5+$  anterior chamber cell AND intraocular pressure  $< 24$  mmHg AND no cornea edema AND no active KPs (day 7, 21).

Trial II: Primary Endpoint: Proportion recurrent inflammation ( $\geq 1+$  anterior chamber cell at any study visit) over 12 months

Secondary Endpoints:

- Prevalence of CMV associated with recurrence of uveitis

1a. The Aim 1 primary outcome **viral load after 7 days of treatment** will use the results from quantitative PCR at 7 days of treatment or placebo therapy (day 7 of trial). All quantitative PCR viral loads will undergo base-10 logarithm-transformation, with units converting from IU/mL to log IU/mL. Log-transformed viral loads will be used because the range of viral loads can be wide and dealing with very large and very small numbers is handled more efficiently using a logarithmic scale. Such normalization of the distribution of viral loads is consistent with standard practice in viral load analyses.

1b. **Clinical outcomes and inactivity:** At each study visit participants will be clinically examined for ocular outcomes including AC inflammatory cells, intraocular pressure, and visual acuity. A study ophthalmologist will make a clinical determination as to whether the patient's inflammation is considered inactive. Clinical outcomes and the proportion of participants that

achieve quiescence by day 7 and 21 will be compared by arm. Patients will also be administered a questionnaire querying when they felt symptomatic improvement in their condition. This analysis will be viewed as hypothesis generating and will be treated as supplementary and in addition to the main finding.

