**2a. Proportion recurrent inflammation over 12 months:** After achieving clinical quiescence, participants will be offered enrollment in Trial II where they would be randomized to long-term suppressive therapy to study the effect on recurrence rate of anterior uveitis. Each participant will be assessed for recurrence at each monthly visit during the 12 months or, alternatively, if participant's experience symptoms of a recurrence, then they will be instructed to call the local site's clinical coordinator to be scheduled for an evaluation within 1 to 2 days. Recurrence of uveitis in CMV is mostly typically symptomatic, so having participants call us is expected to be an effective strategy for catching recurrence of uveitis. If recurrence occurs, aqueous chamber fluid will be collected from participant at the time of recurrence to quantify viral load.

**2b. Prevalence of CMV associated with recurrence of uveitis:** Aqueous fluid obtained in participants exhibiting recurrence of uveitis during Trial II will be submitted for directed polymerase chain reaction testing to determine the proportion of uveitis flares associated with CMV (as compared to “sterile” inflammation).

**3a. Prevalence of mutations conferring antiviral resistance:** The analysis population will include individuals enrolled in both Trials I and II who are randomized to receive oral or topical antivirals in Trial II and experience a recurrent infection. Among patients that experience a recurrent infection (anticipated n=34, see Sample Size section 3.3), we will compare the proportion of infections with antiviral mutations upon recurrence with the proportion with antiviral mutations at baseline.

**3b. Pathogens other than CMV and host transcriptional profile:** (i) In aqueous we will describe the host transcriptional profile in participants with CMV anterior uveitis entering Trial I and in those who fail to enter Trial I due to having negative CMV PCR testing. (ii) We will identify and describe non-CMV pathogens in cases unable to enter Trial I. (iii) We will describe host transcriptional profile in participants during Trial II who have recurrent inflammation.

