### Primary Analysis Trial II

**Aim 2a. Recurrence rate of anterior uveitis over 12 months:** The proposed analysis for sub-Aim 2a (Trial II), which is a clinical outcome, is a log-binomial regression model to compare cumulative inflammatory recurrence (based on anterior chamber cell  $\geq 1+$  cell) between treatment groups. We will censor participants at the first recurrence of anterior uveitis (based on anterior chamber cell  $\geq 1+$  cell) or 12 months. The model includes indicators for the treatment arm and indicators for each site used to stratify the randomization. We will estimate the risk ratios from the model for the two primary comparisons, *oral valganciclovir* vs. *topical ganciclovir 2%*, and *oral valganciclovir* vs. *placebo*. We will use a simulation-based permutation test to estimate p-values, and will report max-T simultaneous confidence intervals and p-values adjusted for the two pair-wise comparisons (*oral valganciclovir* vs. *topical ganciclovir 2%*, *oral valganciclovir* vs. *placebo*). Pre-specified sub-group analyses by sex will be performed.

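### Trial II has a 12-month primary outcome, but SAP 3.6, SAP 3.7 and the Protocol section 3 table still time it at 5 to 7 months

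*SAP*

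**What the plan says.** **Text at 12 months.** SAP 3.3 states that "The primary outcome for Trial II is the proportion of participants experiencing CMV recurrence over 12 months", and its 25% placebo risk is a one-year risk. SAP 6.1 counts a recurrence as 1+ or more "anterior chamber cell at any study visit) over 12 months". The primary model in SAP 6.2 is headed "Recurrence rate of anterior uveitis over 12 months" and censors at first recurrence or 12 months. Protocol 8.1 to 8.3 give the same horizon. Protocol 5.3 sets 12 months of suppressive therapy, and the Protocol schema places Exam 8, the final visit, at month 12.

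**Text at about 6 months.**
- SAP 3.7: "outcome assessments will be conducted every 3 months since beginning of treatment, with a window of 5 to 7 months for the final outcome".
- SAP 3.6: "The final analysis for Trial II will be conducted only after 7 months have elapsed since the treatment of the final enrollee".
- Protocol section 3, in the row identified as the Trial II primary outcome: "Proportion of participants with recurrence at the end of 6months".

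**Visit schedule.** SAP 3.7 has assessments every 3 months. SAP 6.1 says "Each participant will be assessed for recurrence at each monthly visit during the 12 months". The Protocol schema lists months 1, 3, 5, 7, 9, 11 and 12.

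**The concern.** The three short-horizon passages agree with one another: a 6-month endpoint, a window of one month either side, and an analysis once that window has closed. Trial I is built the same way (day 7, window of 5 to 9 days, analysis after 9 days). So this is a second complete timing rule for the primary endpoint, not a single slip. SAP 3.7 is also the only place that gives a window for the Trial II final outcome, so month 12 has none.

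An analyst who follows SAP 3.7 takes final status at 5 to 7 months and misses later recurrences. One who follows SAP 6.1 and 6.2 uses 12 months. A choice made after seeing data could be defended from the documents either way.

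Other rules depend on the horizon: the interim trigger in SAP 3.5 (participants who have reached their primary endpoint), the complete-case definition in SAP 4.2 (a visit within a prescribed period that is not defined), and the 10% missing-data threshold in SAP 6.3. SAP 6.3 does not say whether a participant whose 12 months have not yet elapsed counts as missing. Because the outcome is cell grade at any study visit, the visit schedule also helps to define it.

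**Working it through.** **Inputs from SAP 3.3.** Placebo risk 25%, oral valganciclovir 65%, 28 per arm (105 × 0.8 / 3 = 28), two-sided alpha 0.025 (z = 2.241), two-sample z-test for proportions.

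**Step 1: reproduce the plan's figure.** Mean risk is (0.25 + 0.65)/2 = 0.45.
- SE under the null: √(2 × 0.45 × 0.55 / 28) = 0.1330.
- SE under the alternative: √((0.25 × 0.75 + 0.65 × 0.35) / 28) = 0.1217.
- Power: Φ((0.40 − 2.241 × 0.1330) / 0.1217) = Φ(0.84) = 0.799.

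The stated 40 points at 80% power reproduces.

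**Step 2: the short horizon applied to every participant.** The documents give no time course, so one is assumed: p(t) = 1 − (1 − p₁₂)^((t/12)^k), with p₁₂ = 0.25 or 0.65 and the same shape k in both arms. k = 1 is a constant hazard. At 6 months with k = 1, the risks are 1 − 0.75^0.5 = 13.4% and 1 − 0.35^0.5 = 40.8%. The power formula of step 1 then gives:

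| Month | Risks, k = 1 | Power, k = 1 | Power, k = 0.5 | Power, k = 1.5 |
|---|---|---|---|---|
| 5 | 11.3% vs 35.4% | 45.5% | 63.5% | 30.7% |
| 6 | 13.4% vs 40.8% | 52.9% | 67.3% | 39.4% |
| 7 | 15.4% vs 45.8% | 59.3% | 70.3% | 48.2% |

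At 6 months with k = 1, 80% power would need 49 per arm.

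**Step 3: only the early analysis date of SAP 3.6 applied.** That date is a minimum, and earlier enrollees keep full follow-up. The documents give no accrual period, so uniform accrual over A = 24 or 36 months is assumed. A participant's follow-up is then min(7 + U, 12) months, with U uniform on 0 to A. The share with under 12 months is 5/A: 5/24 = 20.8% or 5/36 = 13.9%. Averaging p(t) over that follow-up with k = 1:

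| | A = 24 | A = 36 |
|---|---|---|
| Unknown 12-month status, placebo / oral | 16.6% / 9.1% | 11.1% / 6.1% |
| Observed risks if counted as non-recurrent | 24.0% vs 63.1% | 24.4% vs 63.8% |
| Power, counted as non-recurrent | 78.0% | 78.7% |
| Observed risks if dropped as missing | 28.8% vs 69.5% | 27.4% vs 67.9% |
| Power, dropped as missing | 74.4% | 76.5% |

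Over k = 0.5 to 1.5, power with non-recurrent coding runs from 77.0% to 79.3%.

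**Step 4: position of the visits.** The 5 to 7 month window contains only Exam 4 (month 5) and Exam 5 (month 7). Exam 8 falls 12 − 7 = 5 months after it closes. Adding the two-month processing minimum in SAP 3.6 gives 7 + 2 = 9 months, still 3 months short of the last enrollee's final visit.

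**The case against.** The governing horizon is not really in doubt. SAP 6.1, SAP 6.2, the one-year planning risk, the treatment period and Exam 8 all say 12 months. The SAP revision history records that version 3 changed the Trial II primary aims and updated 6.1 and 6.2, and it lists no change to 3.6 or 3.7. Those two sections therefore look like leftover text, although that is an inference. An analyst who has read the endpoint and model sections is unlikely to truncate at 5 to 7 months, so the large power losses in step 2 belong to an unlikely reading and to an assumed time course.

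Step 3 can be softened too. If data kept accruing during the two-month processing period, which SAP 3.6 does not say, the cut would be at 9 months. The share with under 12 months would fall to 3/24 = 12.5% or 3/36 = 8.3%, and power with non-recurrent coding would be 79.3% to 79.5% under a constant hazard. On the visit schedule, symptomatic participants are examined between visits, which limits the harm from the differing frequencies.

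All of this is fair on likelihood and size, and the step 2 losses should be read as conditional. It does not remove the contradiction. One of the three passages is the Protocol's own primary-endpoint row, and another is the only outcome window in the plan. Even the 9-month reading analyses some participants before their outcome is known.

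**Conclusion.** The inconsistency is real and must be corrected, because a primary endpoint needs one prespecified time.

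- **12 months governs:** the SAP's 25% against 65% at about 80% power stands, and the three passages are wrong. This covers the SAP figure only; the detectable difference in Protocol 8.2 is a separate matter.
- **The short horizon governs for everyone:** power is 45.5% to 59.3% under a constant hazard, and 31% to 70% over the Weibull shapes.
- **Only SAP 3.6 is used:** power stays at about 74% to 79%, depending on how late enrollees are handled. The bias is small and its direction depends on that handling: risks fall slightly if they are counted as non-recurrent and rise if they are dropped.

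The hazard shapes and the accrual period are assumptions. The conflict between the passages is not.

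**What to change.** - **SAP 3.6:** run the Trial II final analysis only after the last enrollee has completed the 12-month visit or passed its window.
- **SAP 3.7:** replace the 5 to 7 month window with a stated window around month 12.
- **SAP 3.7, SAP 6.1 and the Protocol visit list:** reconcile the three assessment schedules.
- **Protocol section 3 table:** change the Trial II endpoint to recurrence over 12 months.

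The cost is wording in three SAP sections and one Protocol table cell. The earliest final analysis moves 12 − 7 = 5 months later than SAP 3.6 now says, or about 6 if the new window also runs one month past the visit. The 12-month outcome already requires that wait. No extra participants are needed.

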## **4. Statistical Principles**

### **4.1. Confidence intervals and P-values**

The primary analysis for Trial I and Trial II will be conducted with a two-sided alpha of 0.05/2 = 0.025 to account for the two primary comparisons of interest (*oral valganciclovir* vs. *topical ganciclovir 2%*, *oral valganciclovir* vs. placebo). We will report 95% confidence intervals for the estimated differences between groups, on an absolute scale.

We will use a single-step, max-T approach to estimate p-values adjusted for multiple comparisons in each analysis. Alongside unadjusted p-values and 95% confidence intervals, we will present max-T adjusted p-values and simultaneous 95% confidence intervals for differences that account for multiple comparisons.

We will employ a multiple testing hierarchical approach in the following manner:

1. Primary endpointss (alpha = 0.025 each trial)
  - a. Trial I: viral load comparison
  - b. Trial II: Number of recurrences comparison
2. Key secondary endpoints (alpha = 0.025 shared):
  - a. Inflammation control
  - b. Antiviral resistance mutations

Gate-keeping procedure:

Primary endpoints must be significant before testing secondaries

Holm-Bonferroni correction within each family

Truncated testing if primary endpoint non-significant

Family-wise error rate controlled at 0.05 using:

Separate error rates for each trial

Sequential gatekeeping

Multiplicity adjustment within families

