### 2.2. Objectives

#### **Specific Aim 1 (Trial I): To compare CMV viral load and inflammation after randomization to oral valganciclovir, topical ganciclovir 2%, or placebo.**

*1a: We hypothesize that participants randomized to oral valganciclovir will have a lower viral load after 7 days compared to those randomized to either topical ganciclovir 2% or placebo (primary outcome).*

*1b: We hypothesize that a greater proportion of participants randomized to oral valganciclovir will have clinical inactivity at day 7 compared to those randomized to either topical ganciclovir 2% or placebo.*

*1c: We hypothesize RNA sequencing of aqueous humor fluid obtained as part of eligibility determination for Trial I, but negative for CMV, will identify other pathogens and provide host transcriptional profiling.*

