#### 3.3. Sample size

**Primary analysis for Trial I.** The power calculation was based on the primary outcome, base-10 logarithm-transformed CMV viral load. We informed the calculation with viral loads from our recently completed RCT, in which we measured viral load at baseline and 7 days post-treatment. The standard deviation (SD) of log-transformed viral load 7 days post-treatment in this RCT was 0.98. Since the primary analysis will adjust for baseline viral load, we used an estimate of the residual standard deviation, which is  $SD_r = SD\sqrt{1 - r^2}$ , where  $r$  is the correlation between the baseline measure and primary endpoint. In our recently completed RCT, the correlation between baseline and post-treatment viral load was 0.74. Assuming a significance level of 0.05/2=0.025 to account for multiple comparisons and an  $SD_r$  of 0.66 in  $\log_{10}$  viral load, we estimate that we will have 80% power to detect a difference of 0.50 in  $\log_{10}$  viral load (from

3.11 to 2.61) between arms with 35 study participants per arm (117 total allowing for approximately 10% loss to follow up). A reduction of 0.50 in  $\log_{10}$  viral load is equivalent to a  $10^{0.50} = 3.2$ -fold decrease in CMV viral load, which is small but clinically meaningful in the context of CMV antivirals that typically consider 10-fold reductions. This calculation is based on the standard power formula for the T-test using an estimated residual standard deviation.

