### Primary Analysis Trial I

*Aim 1a.* The primary analysis will compare **viral load at 7 days** between each study arm. The Aim 1 treatment effect will be reported as a difference in log IU/mL between the two arms.

We will model mean log viral load using linear regression that includes indicators for treatment arm, indicators for each site used to stratify the randomization, and baseline viral load. We will additionally estimate max-T simultaneous confidence intervals and p-values adjusted for the two

pair-wise comparisons (*oral valganciclovir* vs. *topical ganciclovir 2%*, *oral valganciclovir* vs. *placebo*).

We will examine residuals for approximate normality and to check for outliers and will report the variance within each arm.

Primary analyses will be repeated using multiple imputed datasets as described in Section 6.3 when missing data thresholds are met.

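### SAP 4.1 names single-step max-T and Holm without saying which decides primary significance; if both reach a trial's two contrasts, they can disagree on the weaker one

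*SAP*

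**What the plan says.** SAP 3.4 sets two primary superiority comparisons in each trial: oral valganciclovir against placebo, and oral valganciclovir against topical ganciclovir. SAP 4.1 then gives several statements about multiplicity:

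- The primary analysis "will be conducted with a two-sided alpha of 0.05/2 = 0.025 to account for the two primary comparisons of interest".
- "We will use a single-step, max-T approach to estimate p-values adjusted for multiple comparisons in each analysis", with simultaneous 95% intervals alongside.
- A hierarchy lists families by endpoint. The primary family is Trial I viral load and Trial II recurrences, at 0.025 for each trial. The key secondary family is inflammation control and resistance mutations, sharing 0.025.
- Under the gatekeeping heading: "Holm-Bonferroni correction within each family".
- "Family-wise error rate controlled at 0.05 using" error rates kept separate by trial, sequential gatekeeping and adjustment within families.

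SAP 6.2 attaches max-T to the contrasts again. For Trial I: "We will additionally estimate max-T simultaneous confidence intervals and p-values adjusted for the two" pairwise contrasts. The Trial II text does the same, with permutation p-values. Protocol 8.2 also names max-T for the two comparisons. Hypothesis 1a is that the oral arm "will have a lower viral load after 7 days compared to those randomized to either topical ganciclovir 2% or placebo".

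**The concern.** Nothing in SAP 4.1 links the max-T sentence to the Holm line. Single-step max-T holds both contrasts to one critical value. Holm relaxes the second test once the first is rejected. If both rules cover the same two contrasts, the result for the weaker contrast depends on which sentence the analyst follows, and that choice could be made after the data are seen.

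The weaker contrast matters because hypothesis 1a sets the oral arm against both comparators. The gap also carries forward: the key secondaries are tested only if the primary is significant, and the SAP does not say which p-value settles that or whether one contrast is enough.

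**Working it through.** **Inputs.** SAP 3.3 gives a difference of 0.50 log10, residual SD 0.66, 35 evaluable per arm and two-sided alpha 0.025 per comparison. SAP 3.2 gives 1:1:1 allocation. The contrasts share the oral arm, so their correlation is 0.5. Assumed here: both true differences are 0.50, and 96 degrees of freedom (105 patients less an intercept, 2 arm, 5 site and 1 baseline term, with the six sites of the Protocol synopsis).

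**The plan's own figure.** SD: 0.98 × √(1 − 0.74²) = 0.659. Noncentrality: 0.50 / (0.66 × √(2/35)) = 3.17. The two-sample t-test on 68 df at two-sided 0.025 has critical value 2.29 and gives 80.8% power. The stated 80% reproduces.

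**Decision rules at family-wise 0.05, 96 df**

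- Single-step max-T: reject a contrast if |t| > 2.245 (unadjusted p below 0.0271).
- Holm: the larger |t| must exceed 2.277 (p below 0.025); the other is then compared with 1.985 (p below 0.05).
- Step-down max-T: the larger |t| must exceed 2.245; the other is then compared with 1.985.

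**Worked example.** Raw p-values of 0.010 and 0.040:

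- Holm-adjusted: 2 × 0.010 = 0.020 and 0.040. Both are rejected.
- Single-step max-T-adjusted: 0.019 and 0.073. One is rejected.

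The rules diverge, apart from rare cases, when the stronger contrast has p of at most 0.025 and the weaker lies between about 0.027 and 0.05.

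**How often, and at what cost.** From 2,000,000 simulated Trial I data sets at these inputs:

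| Power at family-wise 0.05 | Single-step max-T | Holm | Step-down max-T |
|---|---|---|---|
| Both contrasts | 71.7% | 79.5% | 79.7% |
| One given contrast | 82.1% | 85.7% | 86.1% |
| At least one contrast | 92.4% | 91.9% | 92.4% |

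Holm alone rejects both in 7.8% of trials; the reverse occurs in about 0.01%.

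**Sensitivity of the both-contrast gap (Holm minus single-step max-T)**

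- One true difference 0.40 or 0.30, the other 0.50: 9.6 points.
- One true difference 0.70 or 1.0, the other 0.50: 6.0 points.
- 39 per arm: 6.8 points.
- SD 0.849, which follows from the Protocol's correlation of 0.50: 9.7 points.
- Family-wise alpha 0.025: 60.8% against 69.6%, about 9 points.

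**Error control of step-down max-T.** The family-wise error is 5.0% with both nulls true. With one null true it is 4.4% when the other effect is 0.50, rising to 5.0% when that effect is very large.

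**Double correction.** If a max-T-adjusted p-value were compared with 0.025 instead of 0.05, power per contrast would fall to about 73.9%, below the planned 80%.

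**The case against.** A reader might infer that the SAP expressly orders both procedures for the same comparisons. It does not. Holm is attached to families listed by endpoint, and max-T to the contrasts. One coherent reading is max-T across contrasts within an endpoint and Holm across the two key secondaries. That reading is open. But with a separate error rate per trial, the only multiple primary tests left within a trial for Holm to act on are the two contrasts, so its role in the primary family is undefined.

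A reader might also infer that the primary analysis is invalid or underpowered. The documents do not support that. The Protocol powers each pairwise comparison, and single-step max-T gives 82.1% against the planned 80%. It is a valid method, and its tests agree with the simultaneous intervals the SAP promises.

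Three further points stand in part:

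- The worked example needs family-wise 0.05. If 0.025 is the family alpha in each trial, Holm's steps are 0.0125 and 0.025, and both rules reject one contrast at p of 0.010 and 0.040. Other p-values still divide them, and the gap remains about 9 points.
- If the only claim were that oral beats both comparators, each contrast could be tested at 0.05 without adjustment (80.4% power). But SAP 3.4 lists two separate comparisons, each of which can be claimed alone, so family-wise control is needed. Step-down max-T, at 79.7%, comes close to that power while keeping it.
- Every extra step-two rejection comes with a single-step interval that includes zero. This is a real cost and a legitimate reason to prefer single-step. Holm carries it too when reported beside those intervals.

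**Conclusion.** The concern holds as an undefined decision rule with a moderate loss of efficiency, not as an invalid analysis. SAP 4.1 does not say what a family contains, which procedure decides primary significance, at what family alpha, or which result opens the gate. If Holm reaches the two contrasts, the rules disagree in about 8% of Trial I data sets at the design inputs.

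The difference of about 8 points applies only to winning both contrasts, and is about 6 to 10 points under other inputs. It rests on reading hypothesis 1a as needing both contrasts. Setting both true differences at 0.50 means that topical is taken to do no better than placebo; the sensitivity cases show that the gap does not depend on this. For one given contrast the gain is about 4 points; for at least one there is none. The figures are for Trial I only. Trial II uses log-binomial regression with permutation p-values, and its gain has not been computed.

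Naming one rule is needed. Choosing step-down max-T is a recommendation on efficiency.

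**What to change.** In SAP 4.1 and 6.2:

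1. Name one deciding procedure for each trial's two primary contrasts, preferably step-down max-T at family-wise 0.05. Compare the larger statistic with the max-T critical value; if it is rejected, compare the other with the unadjusted two-sided 0.05 value. In Trial II apply the same step-down to the permutation p-values.
2. Remove Holm from the primary contrasts and limit it to the key secondary family.
3. State that adjusted p-values are compared with the family-wise alpha, and not again with 0.025.
4. State which primary result opens the gate: one contrast (and which) or both.
5. Keep the single-step simultaneous intervals, and say that a contrast rejected only at step two will have an interval that includes zero.

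The cost is SAP wording and a step-down option in the analysis code; the sample size does not change. If agreement between tests and intervals is valued more, naming single-step max-T as the sole rule also removes the ambiguity, at the power shown above.
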